▣ Protocol Synopsis

Protocol Title	A cluster-randomized, open, prospective, observational study to evaluate the treatment effectiveness and safety of N-acetylcysteine(NAC) inhalation compared with standard treatment in patients with symptomatic acute rhinosinusitis
Sponsor	Boryung Pharmaceutical Co., Ltd.
Participating Site(s) and Investigator(s)	Approximately 12 sites
Study duration	Entire study duration: (enrollment of the first subject to end of observation for the last subject): Around 1 year and 7 months - Enrollment period: Around 1 year and 6 months - Follow-up period: 14 days (± 3 days)
Indication	For patients with symptomatic acute rhinosinusitis (including recurrent acute rhinosinusitis and symptomatic acute-on-chronic rhinosinusitis)
Study Objectives	N-acetylcysteine (NAC), known to have mucolytic and antioxidant effects, is widely used to treat respiratory diseases and manage post-surgery pulmonary complications. It is also administered as a treatment for acetaminophen addiction and a preventive measure for contrast-induced nephropathy (CIN). While NAC inhalation is commonly used for mucolytic purpose for various respiratory disease because it has relatively less side effects compared to oral or injection administrations, it is more used as a part of allopathy than as a major therapy. As a result, there is neither enough relevant clinical data nor specific reference in treatment guidelines. Therefore, this study aims to evaluate the overall treatment effectiveness and safety of NAC inhalation compared with standard treatment, and to perform follow-up observations on administration cases, patient characteristics, and adverse events of NAC inhalation used in real clinical settings.
Phase and Design	A Cluster (study center)-randomized, prospective, observational study.
Investigational Drug	Not applicable
Sample Size and Rationale	Approximately 300 subjects : Re-enrollment is not allowed. - According to similar study results in the past, the difference between N-acetylcysteine (NAC) inhalation and standard treatment in the total score of the investigator's symptomatic severity assessment can be judged as 0.3. In this study, the assumed difference was 1 and the assumed standard deviation was 2.6, conservatively taking the highest value. With the assumed intraclass correlation coefficient (ICC) of 0.005, significance level of 5%, and test power of 80%, the study was to have 6 clusters (study centers) per treatment arm with a total of 12 clusters and 20 subjects in each cluster. it is calculated, as a result, that 120 subjects will be required per treatment arm and 240 subjects in total. Withdrawal is estimated at 20%; therefore, the plan is to recruit 300 subjects in total to have 150 subjects per arm and 25 subjects in each cluster.
Cluster (study center) Selection criteria	① Medical institutions in Korea at the general hospital level ② An otolaryngologist should be available to conduct the study.

Eligibility Criteria – Inclusion Criteria	
 ① Patients are explained about the study objectives and methodologies, and shall express their consent by signing a written agreement for the use of their personal information. ② Male and female patients who are ≥ 18 years old. ③ Symptomatic acute rhinosinusitis patients whose symptoms have been present for more than 1 week and less than 12 weeks; recurrent acute rhinosinusitis patients (acute rhinosinusitis relapsed 3 times or more within 6 months, sub-clinical symptoms between the relapses); or, symptomatic acute-on-chronic (12 weeks or more) rhinosinusitis patients. 
 ➢ Patients display 2 or more symptoms that imply rhinosinusitis infection. The displayed symptoms should include at least one or more cardinal symptoms (nasal congestion or nasal/postnasal discharge). In addition, facial pain/sense of facial pressure, or reduction/loss of smell can also be accepted as relevant symptoms. ④ The total score of the investigator’s symptomatic severity assessment for a patient is 4 or above, and four symptomatic aspects (nasal congestion, nasal/postnasal discharge, facial pain/sense of facial pressure, reduction/loss of smell) are rated in four categories (0=no symptom, 1=mild, 2=moderate, 3=severe). ⑤ Patients have anterior rhinoscopy or nasal endoscopy results, and one or more of the following are observed: 
 ➢ Redness ➢ Edema or mucosal obstruction (mostly in the middle nasal) ➢ Mucopurulent discharge (mostly in the middle nasal) ➢ Nasal polyps
Eligibility Criteria – Exclusion Criteria	
 ① Patients with rhinosinusitis of dental origin. ② Patients with a known chronic pulmonary symptoms including bronchial asthma and chronic bronchitis. ③ Patients with nasal obstruction to the extent that drug administration is difficult. ④ Patients who have received endoscopic sinus surgery within the last 3 months. ⑤ Patients who have shown hypersensitivity or are likely to show hypersensitivity to N-acetylcysteine inhalation components (for the test sites) ⑥ Pregnant or breast-feeding patients. ⑦ Patients who are currently participating in other clinical trials (clinical trials for drugs or medical devices) or are planning to participate in other clinical trials during the duration of this study. ⑧ Patients who are not suitable for study participation upon the investigator’s judgment.
Rhinosinusitis treatment	Patients are randomized to test sites and control sites at the cluster (study center) level. Study centers that are randomized as control sites apply standard treatments for rhinosinusitis excluding NAC inhalation, whereas study groups that are randomized as test sites apply NAC inhalation in addition to standard treatments for rhinosinusitis. This study is an observational study; therefore, the protocol does not present details of the standard treatments or NAC inhalation including dose per administration, number of doses, or administration methods. This study relies on the investigators’ daily medical practices and the patients’ conditions for appropriate decisions to be made. However, NAC can be diluted in sodium chloride or sterile distilled water and no other drugs (for example, bronchodilator) are to be mixed.
Study Methodology	<Overview>

	
12 medical institutions in Korea that meet the inclusion criteria are cluster-randomized (test sites : control sites =1:1). Information about randomization is disclosed to both investigators and subjects. This means both study center investigators and subjects will be aware of the purpose of this study as well as the result of randomization (whether the subjects will receive NAC inhalation or not) from the beginning of the study.
 
Investigators shall obtain voluntary consent for participation in this research from patients who visit their medical institutions with symptomatic acute rhinosinusitis within the study duration. Patients who provided a written consent for the use of their personal information and who satisfy inclusion/exclusion criteria will be given a study enrollment number and available data on these patients will be collected among the predefined study relevant data in the case reports until Day 14 (± 3 days) from the starting day of treatment.
 
<Follow-up observation schedule and the scope of data collection>
 
Data created during subjects' visit to study centers for treatment shall be collected in the case report form. Follow-up observation time points defined below refer to data collection time points. That is, investigators can freely determine patient visit schedules based on the subjects' medical conditions regardless of the follow-up time points defined in this protocol. However, all the data created during the study period and judged to be necessary in relation to this study can be collected in the case report form.
 
In case of various tests including laboratory tests, no separate tests are conducted for this observational research and only those with test results are collected. Following data shall be collected during the study period.
 
 • Demographics of the subjects. • Disease information: diagnosis and start date of symptoms; indications on acute bacterial rhinosinusitis; anterior rhinoscopy/nasal endoscopy test results (for follow-up observation: if available); radiological test results (if available); and, infection source test results (if available). • Past medical history and intercurrent diseases: Examination on intercurrent diseases such as immune deficiency-inducing diseases, chronic diseases including diabetes, lower respiratory diseases, and asthma. Review on anatomical anomaly (if available) that increases the risk of rhinosinusitis, history of sinusitis surgery, and smoking preference. • Recent drug administration: Medication status for use of systemic antibiotics/antifungal agents, immunosuppressants, antihistamine drugs, or steroid for the past 4 weeks. • Body temperature, body weight, height (Enrollment data only for height and weight) • Rhinosinusitis treatment information: information on standard treatment and/or NAC inhalation, surgical procedures (if performed, for example: sinus irrigation or sinuscopy) • Co-medication/procedures: information on other drug administration and surgical procedures during the study period. • VAS assessment: to be indicated on 100mm VAS by subject for overall symptomatic severity. • SNOT-20 (Sino-Nasal Outcome Test) assessment: to be filled-out by subjects. • Investigator's symptom assessment: investigator's assessment for treatment response where each symptom's severity is rated by the investigator.
--	--

	
 Existence of rhinosinusitis complications. Adverse drug reaction related to NAC inhalation. Serious adverse events /adverse drug reactions.
Endpoints	
Primary Endpoint
 
 Change in the total score of the investigator’s symptomatic severity assessment (Day 0, Day 14) (Assessed symptoms: nasal congestion, nasal/postnasal discharge, facial pain/sense of facial pressure, reduction/loss of smell are rated in four categories [0=no symptom, 1=mild, 2=moderate, 3=severe]) 
Secondary Endpoint
 
 Change in the total score of the investigator’s symptomatic severity assessment (Day 0, Day 7) Change in the score of the investigator’s symptomatic severity assessment (Day 0, Day 7, Day 14) Change in SNOT-20 score (Day 0, Day 14) 
Safety Assessment Parameters
 
 Adverse drug reaction (ADR) related to NAC inhalation and incidences/profiles of serious adverse events and ADRs. Rate of subjects who discontinued the study due to ADR and relevant ADR profiles.
Statistical Analysis Methods	
Analysis of primary endpoints
 
Obtain descriptive statistics (average, standard deviation, median, minimum, quartile, and maximum) for the change in the total score* of the investigator’s symptomatic severity assessment by treatment group on Day 14 compared with each time point and baseline (Day 0). Paired t-test shall be used to check intra-group change difference and Two sample t-test shall be used to check inter-group change difference.
 
Also, the same analytic methods shall be used for each cluster (study center).
 
Present ICC, and the Mixed model shall be used to check inter-group difference of the change in the total score of the investigator’s symptomatic severity assessment in consideration of clusters.
 
* The total sum of the investigator’s symptomatic assessment scores (on nasal congestion, nasal/postnasal discharge, facial pain/sense of facial pressure, and reduction/loss of smell).
 
Analysis of secondary endpoints
 
 Change in the total score of the investigator’s symptomatic severity assessment (Day 0, Day 7) Obtain descriptive statistics (average, standard deviation, median, minimum, quartile, and maximum) for the change in the total score of the investigator’s symptomatic severity assessment by treatment group on Day 7 compared with each time point and baseline (Day 0). Paired t-test shall be used to check intra-group change difference and Two sample t-test shall be used to check inter-group change difference.

	
If necessary, in addition, Repeated Measures ANOVA can be conducted to check inter-group difference taking into account of changes in the total score of the investigator's symptomatic severity assessment on baseline (Day 0), Day 7 and Day 14. Multiple regression analysis can also be performed to check factors that influence the change in the total score of the investigator's symptomatic severity assessment. For this, independent parameters may include demographics, baseline characteristics and clinical factors that can be selected in consideration of collected data or clinical characteristics.
 
 • Change in SNOT-20 scores (Day 0, Day 14) Obtain descriptive statistics (average, standard deviation, median, minimum, quartile, and maximum) for individual and total SNOT-20 scores by group on Day 14 compared with each time point and baseline (Day 0). Paired t-test shall be used to check intra-group change difference and Two sample t-test shall be used to check inter-group change difference. 
Analyses of safety data
 
 • Adverse drug reaction (ADR) incidence Present the number of subjects with ADR related to NAC inhalation, ADR incidence, 95% confidence interval for the incidence, and the number of ADR cases. Also, present the number of ADR cases by characteristic (severity, measures taken, progress, and etc.) • Serious adverse event/adverse drug reaction incidence Present the number of subjects with serious adverse event(s) and serious adverse drug reaction(s), their incidence, 95% confidence interval for the incidence, and the number of cases.
--	---

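### Six sites per arm do not deliver the stated 80% power: with 10 between-site degrees of freedom it is about 73% on the plan's own inputs, and lower at any ICC above 0.005

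*Combined protocol and SAP*

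**What the plan says.** The Sample Size and Rationale row of the synopsis states that "the assumed difference was 1 and the assumed standard deviation was 2.6" for the investigator-rated symptom total. It adds an "assumed intraclass correlation coefficient (ICC) of 0.005", a 5% significance level and 80% power. It concludes that "the study was to have 6 clusters (study centers) per treatment arm with a total of 12 clusters and 20 subjects in each cluster", which makes 120 evaluable patients per arm and 240 in all. Allowing for 20% withdrawal, it recruits 25 per site, 300 in total. It gives no formula, sidedness, source for the ICC or allowance for the small number of sites.

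Under Study Methodology, the 12 institutions are randomized 1:1 and allocation is open. Under Rhinosinusitis treatment, "the protocol does not present details of the standard treatments or NAC inhalation", and both are left to each investigator's practice. Under Statistical Analysis Methods, the primary comparison uses a two-sample t-test and also a mixed model that takes account of sites. The section does not say which is decisive or how the mixed model's degrees of freedom are obtained.

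**The concern.** The sample size appears to come from a formula that adjusts the variance for clustering but keeps the critical value for a large number of independent units. With 12 randomized sites, the between-site variance is estimated from 12 − 2 = 10 degrees of freedom, and the larger critical value costs power even when every other input is correct.

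The ICC compounds this. At 0.005 it is very small and unsupported, while the design leaves treatment to each site. If it is higher, the shortfall grows quickly.

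The stake is how a null result is read. A reader told that power was 80% would take non-significance as stronger evidence against a one-point effect than the design supports. The same row of the synopsis judges from earlier results that the difference is 0.3 and then plans for 1, so a null result is a realistic outcome.

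**Working it through.** **Inputs (Sample Size and Rationale):** difference d = 1; SD s = 2.6; ICC ρ = 0.005; m = 20 evaluable patients per site; k = 6 sites per arm; α = 0.05; target power 80%. Sidedness is not stated. Two-sided is assumed because it reproduces the plan's number.

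**1. Reproducing the plan**

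- Independent patients per arm: 2 × [s(1.96 + 0.842)/d]² = 106.1.
- Design effect: 1 + (m − 1)ρ = 1 + 19 × 0.005 = 1.095.
- Clustered: 106.1 × 1.095 = 116.2 per arm; 116.2/20 = 5.81 sites, rounded up to 6, so 120 per arm and 240 in total.
- Withdrawal: 240/0.8 = 300, or 25 per site.
- Standard error: 2.6 × √(2 × 1.095/120) = 0.3512.
- Normal-theory power: Φ(1/0.3512 − 1.96) = Φ(2.847 − 1.96) = 81.2%.

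The plan's figures therefore reproduce. Patient-level degrees of freedom (238) give much the same power, 80.9%.

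**2. Same inputs, 10 between-site degrees of freedom**

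- Noncentrality 2.847 as before; critical t (10 df, two-sided 5%) = 2.228.
- Noncentral-t power = 72.8%. A simulated t-test on site means (400,000 replicates) agrees at 72.9%.
- A difference of 1.09 is needed for 80% power (noncentrality 1.09/0.3512 ≈ 3.1).
- With 20 per site, 7 sites per arm (12 df) would give 80.6%.

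**3. Mixed model, by degrees-of-freedom method**

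These are simulated at ICC 0.005 with 20 per site, setting the site variance to zero whenever its estimate was negative.

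| Method | Power | Type I error |
|---|---|---|
| Fixed 10 df | 68.7% | 2.4% |
| Data-driven (Satterthwaite-like) df | 72.0% | 3.7% |
| Wald z, no correction | 77.7% | 4.6% |

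The Wald z test keeps its level at ICC 0.005, but its type I error rises to 6.0% at 0.02 and 7.2% at 0.05. The two-sample t-test that ignores sites has 83.3% power at ICC 0.005, with type I error of 6.1% there, 9.6% at 0.02 and 16.1% at 0.05.

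**4. Sensitivity to the ICC (20 per site)**

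Values other than 0.005 are illustrative assumptions, not figures from the documents.

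| ICC | Normal formula | 10 df | Difference detectable at 80% power, 10 df |
|---|---|---|---|
| 0 | 84.6% | 76.6% | – |
| 0.005 | 81.2% | 72.8% | 1.09 |
| 0.01 | 78.0% | 69.3% | – |
| 0.02 | 71.8% | 62.9% | 1.23 |
| 0.05 | 56.9% | 48.7% | 1.46 |

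Even with no clustering at all, the 10-df test does not reach 80%.

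**5. Sensitivity to withdrawal (ICC 0.005, 10 df)**

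Power is 72.8% at 20 evaluable per site, 76.4% at 22, 79.5% at 24 and 80.9% at 25. It passes 80% only if nobody withdraws.

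**The case against.** The strongest reply is that the plan makes no calculation error. It applies a standard formula correctly, and 10 degrees of freedom is the reviewer's choice, because the plan names a mixed model and fixes no method. The first part is right: the fault is in the reference distribution, not the arithmetic. The second part means that 73% belongs to a site-level t-test and that the mixed model spans roughly 69% to 78%. It does not restore 80%, since every analysis that respects the randomized unit falls short. The only listed test above 80% gets there by ignoring sites.

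A second reply is that the inputs may be pessimistic. Follow-up is only 14 days, so withdrawal could be below 20%, and the plan calls its SD conservative. An illustrative SD of 2.4 would give 79.3% on 10 df with 20 per site. This is fair, but a power statement has to hold at the inputs it declares, and these inputs do not give 80%.

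A third reply is that nothing in the documents supports a higher ICC. Site-to-site freedom in treatment makes one plausible but does not establish its size. A constant difference between sites in how severely symptoms are rated would largely cancel in a change from baseline. That stands, and the higher ICCs serve only as a sensitivity range. The shortfall at 0.005 does not depend on them.

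**Conclusion.** The concern holds. At the plan's own difference, SD, ICC and evaluable number, power is 72.8% on 10 between-site degrees of freedom, about 7 points below the stated 80%. The chance of missing a true one-point difference is then about 27%, not 20%. It is still about 22% with an uncorrected Wald z test. The conclusion assumes a two-sided 5% test, equal site sizes and the planned 20% withdrawal. It would change only if almost all 25 recruited patients per site were evaluable or the SD were smaller than stated. Any ICC above 0.005 makes the shortfall worse.

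**What to change.** In Sample Size and Rationale, restate the power for 6 sites per arm from the t distribution with 10 degrees of freedom: about 73% for a difference of 1 at ICC 0.005, with a detectable difference of about 1.09 at 80% power. Add one line giving power at ICC 0.01, 0.02 and 0.05 (about 69%, 63% and 49%), labelled as illustrative.

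The cost is one restated figure and one added line, and the stated power becomes less favourable. The sample size, number of sites and conduct of the study need not change.

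### The cluster-adjusted primary comparison names no covariates, although Day 0 score and disease type are available and only six unstratified centres are randomised per arm

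*Combined protocol and SAP*

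**What the plan says.** All references are to the Protocol Synopsis in the combined protocol and SAP.

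- **Eligibility Criteria, inclusion criterion 3.** Three disease types may enter: acute (symptoms for more than 1 and less than 12 weeks), recurrent acute (three or more relapses in 6 months), and "symptomatic acute-on-chronic (12 weeks or more) rhinosinusitis patients". No quota by type is stated.
- **Study Methodology.** Twelve centres are randomised 1:1. No stratification, matching or constraint is stated. Diagnosis and symptom start date are among the data collected.
- **Statistical Analysis Methods, primary endpoint.** Arms are compared by a two-sample t-test on the change in total score, and "the Mixed model shall be used to check inter-group difference of the change in the total score", taking clusters into account. No other term is named for that model, and neither test is designated as primary.
- **Statistical Analysis Methods, secondary endpoints.** A multiple regression may be run if necessary to look for influencing factors; its "independent parameters may include demographics, baseline characteristics and clinical factors". It is optional, does not name disease type and does not mention clusters.
- **Sample Size and Rationale.** "the assumed difference was 1 and the assumed standard deviation was 2.6", with an "assumed intraclass correlation coefficient (ICC) of 0.005" and "6 clusters (study centers) per treatment arm with a total of 12 clusters and 20 subjects in each cluster".

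**The concern.** Patients whose disease has lasted 12 weeks or more may well change by a different amount over 14 days than patients a few weeks into a first episode. Centres need only be at general-hospital level with an otolaryngologist available, so their mix of types can differ. In a cluster design, a difference in mix between centres becomes between-centre variance, which is what limits precision with 12 centres. The Day 0 total score is a natural covariate for a change from Day 0, particularly when entry requires a score of at least 4.

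Both variables are fixed before treatment and need no new data. Leaving them out has two possible consequences. The standard error may be larger than it needs to be, in a design with little slack. And with six centres per arm and no balancing, the arms may differ in case mix by chance, with nothing prespecified to correct the estimate for it.

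**Working it through.** **1. Reproduce the plan's figure.** Inputs from Sample Size and Rationale: difference 1, SD 2.6, ICC 0.005, alpha 5% (taken as two-sided), power 80%, 20 evaluable patients per centre, 20% withdrawal.

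- Individually randomised: n = 2 × (1.960 + 0.842)² × 2.6² / 1² = 106.1, so 107 per arm.
- Design effect: 1 + (20 − 1) × 0.005 = 1.095. Then 107 × 1.095 = 117.2 per arm, or 5.9 centres of 20, rounded up to 6 (120 per arm).
- Recruitment: 240 / 0.8 = 300.
- SE at 120 per arm: √(2 × 6.76 × 1.095 / 120) = 0.351. Power is 81.2% by normal approximation and 72.8% by a t-test on 10 df (12 centres − 2).

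The plan's 120 / 240 / 300 reproduces. Normal-approximation power drops below 80% once the ICC passes about 0.007.

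**2. Add case mix.** The documents give neither the spread of disease types across centres nor their effect on 14-day change, so both are assumed. Let s be the between-centre SD of the share of one type (say acute-on-chronic) and D the difference in mean 14-day change between that type and the rest. Holding the total SD at 2.6:

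- added ICC = (s × D)² / 6.76
- design effect = 1 + 19 × (0.005 + added ICC)
- 95% range of chance shift in the treatment contrast = ±1.96 × s × √(2/6) × D

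| s | D | ICC | Design effect | Power, normal | Power, 10 df | Chance shift (points) |
|---|---|---|---|---|---|---|
| 0 | – | 0.0050 | 1.095 | 81.2% | 72.8% | – |
| 0.10 | 0.5 | 0.0054 | 1.10 | 81.0% | 72.5% | ±0.06 |
| 0.10 | 1 | 0.0065 | 1.12 | 80.3% | 71.7% | ±0.11 |
| 0.10 | 2 | 0.0109 | 1.21 | 77.4% | 68.6% | ±0.23 |
| 0.15 | 0.5 | 0.0058 | 1.11 | 80.7% | 72.2% | ±0.08 |
| 0.15 | 1 | 0.0083 | 1.16 | 79.1% | 70.4% | ±0.17 |
| 0.15 | 1.5 | 0.0125 | 1.24 | 76.4% | 67.6% | ±0.25 |
| 0.15 | 2 | 0.0183 | 1.35 | 72.8% | 63.9% | ±0.34 |

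The chance shift counts only variation in the centres' underlying shares. Sampling 20 patients per centre widens it: at s = 0.10 and a mean share of 30%, the SD of the arm difference in share rises from 5.8 to 8.2 percentage points.

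**3. What adjustment recovers.** A simulation of cluster-level tests (20,000 runs per scenario, mean share 30%, s = 0.10, true effect 1, 10 df) gave the following power.

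| D | Unadjusted | Adjusted for disease type |
|---|---|---|
| 0.5 | 72.8% | 73.2% |
| 1 | 71.4% | 73.7% |
| 1.5 | 70.6% | 75.5% |
| 2 | 69.0% | 77.4% |

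**4. False-positive rate.** With no treatment effect and the same s, the cluster-level test rejected in 4.8% to 5.1% of runs, adjusted or not. The unadjusted patient-level t-test rejected in 6.1% to 7.1%.

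The gain from the Day 0 score is not quantified, because the documents give no correlation between baseline and change.

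**The case against.** Several objections carry weight.

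- **The prognostic premise has no source in the documents.** Nothing says the three types improve differently or that mix varies by centre. A reader might take disease type to be an established prognostic factor here; the text supports only plausible. At D of 0.5 to 1 the loss is about 0.2 to 2 percentage points, and a D of 1.5 to 2 exceeds the treatment effect that the trial is powered for.
- **Possible double counting.** An ICC of 0.005 may already include case mix, since the plan does not say. It could fully do so only while s × D is at most √(0.005 × 6.76) = 0.184. The scenarios with s = 0.15 and D of 1.5 or 2, and with s = 0.10 and D = 2, exceed this alone. For milder ones the planned power may stand, and adjustment would then be a gain, not a repair.
- **A chance imbalance could be read as a spurious drug effect.** That stronger reading fails for the mixed model. The random centre effect carries case-mix variance into the standard error, and the false-positive rate stays near 5%. Imbalance in the realised sample remains uncorrected, which is a matter of precision and of interpreting the estimate.
- **The plan does not exclude covariates.** Mentioning clusters does not list the fixed effects or rule others out. But the only stated route for baseline factors is an optional regression that aims at influencing factors and does not mention clusters, so it is at most partial mitigation.
- **Why these two covariates?** Others, such as polyps or recent antibiotics, could be argued for. Day 0 score and the type that defines entry are the most direct choices.

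**Conclusion.** The point stands as a worthwhile, low-cost improvement, not as a flaw that invalidates the comparison. The stated mixed model leaves out two available, plausibly prognostic covariates in a design with six unstratified centres per arm and normal-approximation power of 81.2%. The harm is lost precision and uncorrected chance imbalance.

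The size rests on assumptions. With s of 10 to 15 percentage points and D of 0.5 to 2 points, power ranges from essentially unchanged to a loss of about 8 to 9 percentage points (81.2% to 72.8% by normal approximation, 72.8% to 63.9% on 10 df). The lower starting value on 10 df comes from having 12 centres and is not caused by case mix.

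A reader might also infer that the three types should not be pooled. Nothing here supports that; the population and endpoint can stay. The false-positive concern belongs to the unadjusted t-test, which matters because the plan does not say which test is primary.

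**What to change.** In Statistical Analysis Methods, under the primary endpoint:

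1. Name the mixed model as the primary treatment comparison and label the two-sample t-test as descriptive or supportive.
2. Specify fixed effects for arm, Day 0 total score and disease type (acute, recurrent acute, acute-on-chronic), a random centre intercept, and small-sample degrees of freedom for 12 centres, for example Kenward-Roger.
3. State a rule that assigns each patient to exactly one type at entry, from the recorded diagnosis, symptom start date and the elements of inclusion criterion 3. As worded, a recurrent patient in a 1 to 12 week episode fits two categories. Because investigators know the allocation, the rule should use recorded entry data and leave no room for later judgement.
4. Tabulate disease type by centre and arm in the baseline summary.

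No subgroup claim is needed. The cost is a short SAP amendment, one derivation rule, and three extra patient-level parameters (one for Day 0 score, two for disease type) estimated from about 240 patients. Data collection, population and endpoint do not change. If disease type turns out to be weakly prognostic, almost nothing is lost.

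### Exclusion 3 depends on difficulty of giving an unnamed drug, so it may be applied more strictly at test sites and unbalance the arms on nasal obstruction

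*Combined protocol and SAP*

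**What the plan says.** In the synopsis, under Eligibility Criteria – Exclusion Criteria, the third criterion removes "Patients with nasal obstruction to the extent that drug administration is difficult". It names neither a drug nor an arm. Two items later, the hypersensitivity criterion is restricted to one arm: "Patients who have shown hypersensitivity or are likely to show hypersensitivity to N-acetylcysteine inhalation components (for the test sites".

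The row on rhinosinusitis treatment says: "Study centers that are randomized as control sites apply standard treatments for rhinosinusitis excluding NAC inhalation". Test sites, by contrast, "apply NAC inhalation in addition to standard treatments for rhinosinusitis". Routes are left open on both sides, because "the protocol does not present details of the standard treatments or NAC inhalation including dose per administration, number of doses, or administration methods". The row for the investigational drug reads as not applicable, so it does not supply the missing name.

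Under Study Methodology, sites are randomized first and "Information about randomization is disclosed to both investigators and subjects". Patients are then consented and checked for eligibility at a site whose arm is known.

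The primary endpoint is the change from Day 0 to Day 14 in the total of four investigator-rated symptoms: "nasal congestion, nasal/postnasal discharge, facial pain/sense of facial pressure, reduction/loss of smell are rated in four categories", each scored 0 to 3. The Statistical Analysis Methods give a two-sample t-test on the change and a mixed model that allows for clusters. Neither names a baseline covariate. The synopsis describes no screening log.

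**The concern.** A criterion about difficulty of giving a drug can be judged only against some particular drug. A test-site investigator has an obvious one in mind, the NAC inhalation that the patient is about to receive. A control-site investigator has only the local standard treatment, by whatever route that site uses. Where that route is not nasal or inhaled, the same obstruction may raise no difficulty. One rule can then give different answers by arm, and the investigator knows the arm when applying it.

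Nasal obstruction is close to what the trial measures. Nasal congestion is one of the four items in the primary score and also counts towards the entry threshold of 4. If obstructed patients are kept more often at control sites, the arms may start with different congestion and change differently over 14 days without any effect of NAC. A random effect for centre handles correlation within centres. It does not remove a difference in selection that runs along the allocation.

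**Working it through.** **Is the criterion common to both arms?** Exclusion 5 is expressly limited to test sites and exclusion 3 is not. The protocol marks an arm-specific exclusion when it wants one, so exclusion 3 is meant for all 12 sites. What is missing is the reference: no row says which drug is meant or how a control site should judge it.

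**The plan's own figure** (Sample Size and Rationale: difference 1, SD 2.6, ICC 0.005, significance level 5%, power 80%, 20 subjects per cluster; a two-sided test is assumed because sidedness is not stated).

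- Unclustered n per arm: 2 × [2.6 × (1.960 + 0.842) / 1]² = 106.1.
- Design effect: 1 + (20 − 1) × 0.005 = 1.095.
- 106.1 × 1.095 = 116.2 per arm; 116.2 / 20 = 5.81 clusters, rounded up to 6, so 120 per arm and 240 in total.
- 240 / 0.8 = 300 after 20% withdrawal. The stated figures reproduce.
- Standard error of the difference: 2.6 × √(2 × 1.095 / 120) = 0.351. Power at a difference of 1: Φ(1 / 0.351 − 1.96) = 81%.

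**What unequal application could do.** The documents give none of the inputs below; all are assumptions, and all suppose that the criterion removes patients at test sites only. If control sites remove some of the same patients, the shift shrinks in proportion.

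*Model A: share removed × difference in their 14-day change.* With a share of 10–20% and a difference of 1–2 points, the shift is 0.1 × 1 = 0.1 to 0.2 × 2 = 0.4.

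*Model B: through the baseline score.* Let f be the share removed (5–20%), D the excess of their baseline total over that of the patients retained (1–3 points), and b the slope of improvement on baseline (0.3–0.7). Baseline imbalance is f × D and the shift in the difference in change is b × f × D.

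| Case | f | D | b | Baseline imbalance | Shift | Power if against NAC |
|---|---|---|---|---|---|---|
| Low | 5% | 1 | 0.3 | 0.05 | 0.015 | 80% |
| Middle | 10% | 2 | 0.5 | 0.20 | 0.10 | 73% |
| High | 20% | 3 | 0.7 | 0.60 | 0.42 | 38% |

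Power is Φ((1 − shift) / 0.351 − 1.96). For the middle case, 0.9 / 0.351 − 1.96 = 0.60, and Φ(0.60) = 73%. At the top of Model A, a shift of 0.4 leaves 0.6, and Φ(0.6 / 0.351 − 1.96) = 40%.

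**Direction.** Model B works against NAC, because the test arm has less room to improve. If heavily obstructed patients improve less, for instance because the obstruction is fixed, the sign reverses and NAC is favoured. With no true effect, a shift of 0.10 in either direction raises the two-sided rejection rate from 5% to 5.9%, and one of 0.42 raises it to 22%.

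**The case against.** The strongest case against is that the text treats the arms alike. With no arm restriction, and with exclusion 5 as a contrast, exclusion 3 binds control sites too. The drug is not defined as NAC, so a control site using nasally delivered treatment may exclude the same patients. Test-site patients also receive standard treatment, and because NAC administration methods are left open, the documents do not show how far obstruction would impede it. Every input to the size calculation is assumed. The root problem is broader: screening follows open allocation, and exclusion 8 leaves further room for discretion.

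Most of this stands, and it limits the point. A reader might infer that the most congested patients are screened out of the test arm, or that a patient with congestion rated 3 is excluded at a test site and enrolled at a control site. The documents support neither statement. Unequal application is a risk, not a feature of the text. A rating of 3 is nowhere equated with obstruction that hinders drug administration, and inclusion criterion 5 accepts mucosal obstruction and polyps as qualifying findings.

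The objection does not supply the missing reference. That the sponsor meant a common rule does not tell a control site what to judge against. That other routes to selection exist is no reason to leave this one open.

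**Conclusion.** The concern holds as a risk. Exclusion 3 is meant to be common but rests on an unnamed drug; the obvious candidate is given in one arm only, and the judgement is made with allocation known. It may therefore be applied more strictly at test sites, and neither planned analysis would remove the resulting difference.

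Size and direction are unknown. On the assumed inputs the shift runs from near zero (0.015) to about 0.4 points against a planned effect of 1. The middle case of 0.10 is a third of the 0.3 that the plan cites from past studies. The upper end needs every assumption at its maximum and application in one arm only. The stated sample size is not affected. This is a cheap improvement: it closes a route to selection that cannot be fully repaired after enrolment and, without a log, cannot be measured.

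**What to change.** - Reword exclusion 3 so that it refers to one stated reference and is judged identically at every site, regardless of allocation. One example is obstruction that would make NAC inhalation difficult, whether or not NAC will be given.
- Log the number excluded under this criterion by centre.
- Report Day 0 nasal congestion by arm. The item is already rated at entry, so no new data are needed.
- Include the baseline total score as a covariate in the mixed model. This reduces a selection difference but does not remove it, so it supplements the rewording and cannot replace it.

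The cost is one sentence in the eligibility criteria, one screening-log item and one model term. Control sites lose a few patients whom they might otherwise have enrolled. Judgement with allocation known remains partly subjective, at control sites especially, where investigators would be assessing difficulty with a treatment that they will not give; the log by centre is what would show whether that matters.
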